10.0 Data Management

- **Confidentiality protection:** The data from test results will be de-identified once it has been collected and before it is stored. This means individual results would not be able to be linked to the participant by others who review the results of this research. The linkage between participant codes and identities as well as all other identifiable

information including consent forms will be stored in a locked room and be accessible only to the study personnel.

- Statistical analysis: For Primary Aim of feasibility and safety, we will compare rates of compliance and device-related adverse events between the treatment and control conditions using the test of non-inferiority. For safety, we will analyze the data using the “intent to treat” paradigm. The meaningful difference in adverse events to detect between the treatment and control is 20% for the following reason. For a regulatory approval, a safety level similar to a comparable FDA-approved device is desired. One such device, with availability of safety data, is a Bioness electrical stimulator for foot drop: It has a 21% higher likelihood for adverse events compared to a standard ankle foot orthosis (Kluding et al. 2013). Based on power analysis below, we will be sufficiently powered to statistically discern different rates of adverse events if more than 3 out of 24 participants experience adverse events in the treatment vs. control condition. In other words, if 3 or less participants out of 24 experience adverse events in the treatment vs. control condition, we will deem TheraBracelet safe for the purpose of an FDA approval. We will verify that there is no order effect using exact binomial tests.
- For feasibility, compliance will be defined as participants’ use of the device for at least half the prescribed time. The reason is that 4 hours/day is still a substantial use of this assistive device in daily living, and will provide sufficiently useful information about feasibility of TheraBracelet. Similarly with the analysis for safety, if 3 or less participants out of 24 are incompliant in the treatment vs. control, we will conclude that TheraBracelet is as feasible as wearing a non-vibrating wristband. The cumulative hours of device usage will also be examined for both conditions to inform the general usage trend.
- For the secondary outcome of durability of TheraBracelet’s instant effect, the hypothesis will be tested using repeated measures ANOVA for each hand function measure, with factors of vibration (on/off), condition (treatment/control), evaluation time (1-5), and their interactions. A significant main effect of vibration, with improved hand function with vibration on vs. off, with non-significant interactions of vibration×evaluation time and vibration×condition, would indicate durability over a month. In contrast, a lesser extent or abolishment of the instant effect toward the later evaluations or for the treatment condition, with significant interactions of vibration×evaluation time or vibration×condition, would indicate desensitization. In that case, the time point at which the instant effect wanes will be examined using Tukey type posthoc pairwise comparisons.
- A possibility exists that instant enhancement of hand function with TheraBracelet may trigger more use of the affected hand in daily living, which, when accumulated over time, might lead to improvement of the innate hand function (without vibration). This is analogous to cane users who may walk more with canes than without, and thus build greater lower limb abilities over time. Thus, change in the innate hand function will be examined. A significant effect of condition×evaluation time, with greater improvement of the innate hand function for the treatment vs. control, will suggest a therapeutic effect of TheraBracelet for secondary investigation.
- Impact of TheraBracelet on activities of daily living and quality of life will be assessed using repeated measures ANOVA for the SIS and SS-QoL, with the main effect of condition.

- Power analysis: The sample size for the primary outcome of safety was determined for testing hypothesis of non-inferiority using a 2×2 crossover at 80% power and 5% significance level. A sample size of 24 (12 in each condition at randomization) provides sufficient power to conclude non-inferiority within a difference in adverse events of 20% between the discordant pairs (those who are safe with control but unsafe with treatment vs. those with the opposite), assuming a total of 10% discordance rate (proportion of participants with different responses for the two conditions) and a 90% safe rate for the control. That is, we will be powered to statistically conclude non-inferiority (hence safety) if 3 or less out of 24 participants have adverse events in treatment vs. control. For the Secondary Aim involving repeated measures ANOVA, with the effect size of $f=0.25$ for the Box and Block from our previous study, (Seo et al., 2014) a sample size of 19 is needed assuming a conservative correlation of 0.3 across evaluation times, for 80% power and 5% significance level. Thus, we will aim to obtain data from 24 participants. Considering that some may be found ineligible after enrollment, a total of 30 recruitment is proposed.
- Data sharing: Only de-identified coded data will be reported and/or shared with the public in publications, in ClinicalTrials.gov, or upon written request.

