1.0 Objectives / Specific Aims

- Objectives: To determine the feasibility and safety of using this assistive device, TheraBracelet, every day during waking hours, and to determine if TheraBracelet's instant effects are sustained during prolonged use.
- Design: Community-dwelling chronic stroke survivors will be randomly assigned to either the treatment or control condition for the first month, followed by a 2-week washout period and then crossover to the other condition. In both the treatment and control conditions, participants will be instructed to wear the device for at least 8 hours/day every day during their normal daily activity and come to the laboratory for evaluation prior to and each week of using the device (for a total of 5 evaluations over 4 weeks). The device will deliver vibration (treatment) or no vibration (control). Double-blinding will be possible because the treatment vibration is imperceptible (i.e., subthreshold).
- Primary Aim: Determine the feasibility and safety of using TheraBracelet daily for a month. For feasibility, compliance in using the device will be assessed by weekly self-reports of usage. Hypothesis: TheraBracelet will have a feasibility level comparable to wearing a non-vibrating wristband. To determine safety, participants will be examined at each weekly visit for any worsening of hand sensation, dexterity, grip strength, upper limb pain, spasticity, and wrist skin irritation. Adverse events will be recorded and categorized by severity (minor, moderate, and serious) and device relevance (related to device use or not). Adverse event frequency will be compared between conditions, and with a comparable FDA-approved device, Bioness electrical muscle stimulator. Hypothesis: TheraBracelet will have a safety level equivalent to or better than the comparable FDA-approved assistive device.

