- **Feasibility:** We will compare user compliance in using the device in the treatment vs. control. Compliance will be assessed using self-reports. Participants will bring home a device usage log, record time at which they put on and take off the device every day, and submit the log during the weekly evaluation. Study personnel will record which hand the participant is wearing the device (right vs left) at the beginning of the weekly evaluation session. During their final session, participants will complete a technology acceptance questionnaire to evaluate their experience using the device. Additionally, a pedometer function will be run in the watch to obtain a total number of steps for a week, which can provide a rough estimate of the wear time. Participants will also wear the device while completing a 10-meter walk test during their initial visit. Walking speed and the pedometer reading will be recorded when the test is complete.
- **Safety:** We will compare the rate of occurrence of adverse events in the treatment vs. control condition. The measures of adverse events will include worsening of hand sensation, hand strength, hand dexterity, upper limb pain level, spasticity, and wrist skin irritation. Specifically, hand sensation will be assessed using the Monofilament Test, the Two-Point Discrimination Test, and verbal report of any numbness and tingling. Hand sensation will be determined to have deteriorated if any of these hand sensation test results declines by a category (e.g. "normal" to "diminished light touch" for the Monofilament Test with a change more than two points; "no" to "yes" for numbness and tingling). Hand strength will be determined to have deteriorated if grip strength declines by more than 20% from the baseline (which is approximately 2 standard deviation of the population grip strength data) and more than minimal

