detectable change (MDC) (also known as the smallest real difference, Chen et al 2009). Hand dexterity will be determined to have deteriorated if the Nine Hole Peg or Box and Block Test score worsens by more than 20% (approximately 2 standard deviation of the population data) and MDC (Chen et al 2009). Hand strength and dexterity measurement will be performed three times during the baseline testing. Upper limb pain will be assessed using the visual analog pain rating scale (0 to 10). Upper limb pain will be determined to have increased if the pain level indicated on the visual analog pain rating scale increases by more than 2. Spasticity will be show assessed using the Modified Ashworth Scale (MAS). Spasticity will be determined to have worsened if MAS increases by more than 1 point (equivalent to the effect size of botulinum toxin A). Wrist skin irritation and increased swelling, if there is any, will be noted. Rigorous safety criteria will be used in which adverse events will be noted if any of the measures (hand sensation, strength, dexterity, pain, spasticity, skin irritation, swelling) worsens at any of the four evaluation times compared to the baseline. The co-investigator and study neurologist, [name], will meet with each participant in person or via teleconference to interview the participant regarding safety related to wearing the device.

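### The primary safety test is limited to device-related adverse events, but its margin, decision rule and power basis refer to all adverse events, and relatedness has no criteria

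*Combined protocol and SAP*

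**What the plan says.** All references are to the combined protocol and SAP.

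- **Section 10.0, Statistical analysis, test sentence:** "we will compare rates of compliance and device-related adverse events between the treatment and control conditions using the test of non-inferiority". This is the only place where the tested event set carries a relatedness limit.
- **Same bullet, margin:** "The meaningful difference in adverse events to detect between the treatment and control is 20" percent. The foot-drop stimulator figure behind it (21%) is also for adverse events, with relatedness not stated.
- **Same bullet, decision rule:** the device is deemed safe "if 3 or less participants out of 24 experience adverse events in the treatment vs. control condition".
- **Section 1.0, Primary Aim:** events are to be categorised by severity and by "device relevance (related to device use or not"). The next sentence begins "Adverse event frequency will be compared between conditions", with no limit.
- **Section 9.0, Safety:** "We will compare the rate of occurrence of adverse events in the treatment vs. control condition". Further on, "adverse events will be noted if any of the measures" worsens at any of the four evaluations compared with baseline. Seven measures are listed and no causal condition is attached. The study neurologist will also "interview the participant regarding safety related to wearing the device".
- **Section 9.0, Protection against risk:** the monitored worsenings are described as the safety outcome measures of the primary aim.
- **Section 10.0, Power analysis:** the 20% difference is again in adverse events, with 10% discordance and a 90% safe rate on control.
- **Section 11.0:** the DSMB reviews the listed worsenings and any other adverse events, related or not.

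**The concern.** The primary safety comparison has two candidate event sets, and they can give different answers from the same data. One is every listed worsening. The other is the subset that someone judges to be caused by the device.

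The second set depends on a judgement that the plan does not define. Section 1.0 supplies a yes/no label. Section 9.0 supplies an interview, but no criteria and no stated link between interview and label. No section names who assigns the label. Section 12.0 says that no side-effect information is known for all-day use over a month, so the assessor has no reference profile to judge against.

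The control condition is there, according to section 9.0 (Study design), to account for worsening that is part of the natural course after stroke. Comparing all events between randomised conditions already does that. A relatedness filter would try to do it again by opinion. If it discards events that vibration really caused, it shrinks the observed excess, and in a non-inferiority test that favours a conclusion of safety. Section 10.0 ties that conclusion to regulatory approval.

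**Working it through.** **1. Reproduce the plan's sample size.** Inputs from section 10.0 (Power analysis): margin δ = 0.20, discordance 0.10 (taken as 0.05 each way), 5% level, 80% power. The level's side and the test statistic are not stated. For a paired score test with restricted maximum likelihood estimates:

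N = [ (z_α √(2q + δ − δ²) + z_β √0.10) / δ ]², where q is the restricted estimate of the control-only probability, here 0.0231.

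One-sided 5%: N = [ (1.645 × √0.2062 + 0.842 × √0.10) / 0.20 ]² = 25.7, so 26. Exact enumeration at N = 24 gives 82.4% power. At one-sided 2.5% the formula gives 34, and power at 24 is 62.9%. The plan's 24 therefore fits a one-sided 5% score test best, and that test is used below as an assumption. There is no arithmetic error in the sample size.

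**2. Can one relatedness call change the answer?** With b treatment-only and c control-only participants among 24:

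z = (b − c − 24 × 0.20) / √[24 (2q + 0.16)]

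| b vs c | Numerator | q | z | One-sided p | Non-inferior at 5%? |
|---|---|---|---|---|---|
| 3 vs 1 | −2.8 | 0.0250 | −2.8/√5.04 = −1.247 | 0.106 | No |
| 2 vs 1 | −3.8 | 0.0215 | −3.8/√4.873 = −1.721 | 0.043 | Yes |
| 2 vs 0 | −2.8 | 0 | −2.8/√3.84 = −1.429 | 0.077 | No |

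Reclassifying one treatment-only participant (row 1 to row 2) gains non-inferiority. Reclassifying one control-only participant (row 2 to row 3) loses it.

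**3. Limits of that example.** At one-sided 2.5% none of the three rows passes, so nothing flips. Under the 3-of-24 rule, treatment-only counts are 3, 2 and 2 and net counts are 2, 1 and 2. All satisfy the rule on either reading, so nothing flips there either.

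**4. Effect of discarding true device events.** This is an illustration; none of its inputs comes from the documents. Take a true excess equal to the margin: 25% treatment-only and 5% control-only. Let s be the share of participants with vibration-caused events kept, and k the share with background events kept (0 to 1). The filtered probabilities are 0.05k + 0.20s (treatment-only) and 0.05k (control-only); concordant pairs are left unfiltered. Probability of falsely concluding non-inferiority:

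| Share kept (s) | One-sided 5% | One-sided 2.5% |
|---|---|---|
| No filter | 4.7% | 2.5% |
| 100% | 3.3–4.7% | 0.5–2.5% |
| 75% | 11–13% | 2–7% |
| 50% | 26–30% | 8–16% |

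Ranges are over k. With perfect attribution (s = 100%) there is no material inflation. Retention per event is milder: if each affected participant had two independently judged events, 50% per event becomes 1 − 0.5² = 75% per participant.

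**5. Power if all events are used.** Equal true rates, one-sided 5%, N = 24: 82% at 10% discordance, 79% at 12%, 68% at 18%, 57% at 25%. These are general sensitivities, not forecasts for this endpoint.

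**The case against.** The test sentence is the one that specifies the analysis, and section 1.0 plans a relatedness label, so later uses of adverse events could be shorthand for the device-related ones. Section 12.0 leans the same way: it speaks of risks that may be associated with vibration being tested as the primary safety outcomes. The statement under Protection against risk names what is monitored and does not address relatedness. This stands as far as it goes. The shorthand reading cannot be excluded, and a reader who inferred that section 9.0 rules it out would be going beyond the text.

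The worked example uses a score test that the plan does not name, and it does not flip at one-sided 2.5% or under the 3-of-24 rule as read above. That stands. That one participant can matter near the boundary is also true of any binary endpoint in 24 people.

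A reader might infer that the limit to device-related events necessarily biases the trial towards safety. The documents do not support that. The filter can work in either direction, perfect attribution causes no inflation, and the retention shares behind the larger error rates are assumed.

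A reader might also infer that blinding protects the judgement. Section 11.0 blinds experimenters and participants but gives the DSMB the condition assignment. With no assessor named, a blinded relatedness call is plausible but not stated. Even a blinded assessor could label vibration-caused events as unrelated.

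**Conclusion.** The inconsistency is real and concerns the primary safety endpoint. One sentence limits the test to device-related events; the margin, the decision rule, the Primary Aim, the safety methods and the power analysis do not. The weight of the text favours all events, but no available section settles it. Relatedness has neither criteria nor a named assessor.

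Its consequence is that an analyst could choose between two primary results, in either direction. The demonstration in 24 pairs (p = 0.106 to 0.043, and 0.043 to 0.077) rests on an assumed one-sided 5% score test. The 11–13% and 26–30% false non-inferiority rates are conditional illustrations and should not be read as estimates for this trial. DSMB review of all events by condition protects participants but does not determine which set the primary test uses. The point should be corrected before analysis.

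**What to change.** Use one event set in the test, the margin, the decision rule and the power inputs. The set that fits sections 1.0 and 9.0 and the power analysis is any worsening listed under Safety in section 9.0, at any of the four evaluations, regardless of judged relatedness. To adopt it:

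- Delete the device-related limit from the adverse-event test in section 10.0 (Statistical analysis).
- Report device-related events by condition as supporting, using written relatedness criteria applied by a named role blinded to condition.
- Report the other adverse events covered by section 11.0 by condition.
- State in section 10.0 (Power analysis) which event set the 10% discordance and 90% safe rate describe; if they do not describe the chosen set, restate them and the power.

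If the sponsor prefers device-related events as primary, that also removes the ambiguity, provided that the criteria and the blinded assessor are fixed before analysis and the all-event comparison is reported beside it.

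The cost is wording and a short set of criteria, with no new data. The downside of the all-event set is a less favourable event rate and, if its discordance exceeds about 10%, power below the planned 80% (working, step 5).

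### The safety non-inferiority comparison names only intent to treat and ignores the wear data, so low wear biases it towards a conclusion of safety

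*Combined protocol and SAP*

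**What the plan says.** The objective in section 1.0 is "To determine the feasibility and safety of using this assistive device, TheraBracelet, every day during waking hours". Section 9.0 asks for at least 8 hours of wear a day for a month in each condition. Participants log on and off times daily, and a pedometer gives a rough check on wear. The same section records an adverse event if any safety measure worsens from baseline at any of the four weekly evaluations.

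For the analysis, section 10.0 says "we will compare rates of compliance and device-related adverse events between the treatment and control conditions using the test of non-inferiority", and then "For safety, we will analyze the data using the “intent to treat” paradigm". It names no per-protocol, as-treated or exposure-related safety analysis. Under feasibility, "compliance will be defined as participants’ use of the device for at least half the prescribed time", which the plan equates to 4 hours a day. Cumulative hours are to be examined only to describe usage.

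The power paragraph of section 10.0 sets the test "using a 2×2 crossover at 80% power and 5% significance level", with a margin "within a difference in adverse events of 20% between the discordant pairs", "assuming a total of 10% discordance rate (proportion of participants with different responses for the two conditions) and a 90% safe rate for the control". Section 10.0 also gives a count rule: the device is deemed safe if 3 or fewer of 24 participants have adverse events in treatment versus control.

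**The concern.** In a superiority trial, non-adherence under intent to treat usually works against the sponsor's claim. In a non-inferiority safety comparison it works for the claim. Participants who hardly wear the vibrating device have little chance of showing harm from it, so the difference between conditions moves towards zero.

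The device is self-applied at home, so wear may vary widely. The data needed to see this are collected, and a compliance threshold is already defined, but neither is linked to the safety result. The plan intends that result to support a regulatory safety claim. As written, the comparison answers whether being given the device is acceptably safe. The stated objective asks whether using it daily is.

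**Working it through.** **Inputs from section 10.0.** n = 24 participants, each serving as own control; margin δ = 0.20; 5% significance; 80% power; 10% total discordance. With no true difference, the discordance splits into 5% with an event on treatment only and 5% on control only.

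**Assumptions.** The plan names neither the test statistic nor its sidedness. I use the paired score test for a difference in proportions (Tango/Nam), one-sided 5%.

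**Test.** Let b be the number with an event on treatment only and c the number on control only.

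- z = (b − c − nδ) / √{n[2q + δ(1 − δ)]}
- q = [√(B² − 4AC) − B] / (2A)
- A = 2n, B = −b − c + (2n − b + c)δ, C = −cδ(1 − δ)
- Conclude non-inferiority if z ≤ −1.645.

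Example: b = 1, c = 0 gives q = 0 and z = (1 − 4.8)/√(24 × 0.16) = −3.8/1.96 = −1.94, which passes. b = 2, c = 0 gives −2.8/1.96 = −1.43, which fails.

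**Reproducing the plan's sample size.** The probabilities of all (b, c) pairs that pass are summed under a multinomial with cells 0.05, 0.05 and 0.90. Power at n = 24 is 82.4%, and the smallest n reaching 80% is 23. The asymptotic formula gives 25.7, so 26. Both are close to the plan's 24. Of the variants tried, only this one comes within 2 of it: the score test at one-sided 2.5% needs 34, and the Wald test needs 16 (one-sided 5%) or 20 (one-sided 2.5%).

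**Dilution.** Suppose real wearers carry a true excess of 20 points, exactly the margin. Let a share f of participants be unexposed in the treatment month and have no excess. Then:

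- P(event on treatment only) = 0.05 + 0.20(1 − f)
- P(event on control only) = 0.05

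| Unexposed share f | Intent-to-treat excess | P(treatment only) | False non-inferiority |
|---|---|---|---|
| 0 | 20 points | 0.250 | 4.7% |
| 12.5% (3 of 24) | 17.5 points | 0.225 | 7.5% |
| 25% | 15 points | 0.200 | 11.7% |
| 50% | 10 points | 0.150 | 26.3% |

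The 3-of-24 row uses the count in the plan's own feasibility rule.

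**Partial exposure.** If those 3 of 24 carry half the excess, P(treatment only) = 0.05 + 0.20 × (1 − 0.125 × 0.5) = 0.2375, and the error is 5.9%. If half the sample carries half the excess, the effective f is 0.5 × 0.5 = 0.25, and the error is 11.7%.

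**Larger harm.** With a true 25-point excess, the error is 1.7% at full wear, 3.2% with 12.5% unexposed and 17.8% with 50% unexposed.

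**The count rule.** If the 3-or-fewer rule governs and is read as b − c ≤ 3, the corresponding rates for a 20-point excess are 30.3%, 39.0%, 48.9% and 70.4% for f = 0, 12.5%, 25% and 50%. The level differs, but the direction is the same.

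**The case against.** Five counter-arguments deserve weight.

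- **A reader might infer that every poor wearer is scored as safe.** Section 9.0 does not support this. Events are recorded at each weekly visit whatever the wear, so a low wearer counts as safe only if no adverse event is noted at any of them. Someone who stops wearing the device because of an event still counts as unsafe under intent to treat, which is a good reason to keep that analysis. This stands.
- **A reader might take 26% as the trial's error rate.** The documents predict no adherence rate. Non-compliance means under 4 hours a day, which can still be hours of exposure, so zero excess in non-wearers is an upper bound on dilution. This stands: the larger figures are scenarios.
- **The score test may not be the operative rule.** The plan does not name it, and the 3-or-fewer count gives much higher error even at full wear. The percentages above therefore depend on the 5% test governing. The mismatch between count and test is a separate problem.
- **The feasibility test is a safeguard.** If its 3-of-24 limit is an absolute count, widespread non-wear would fail feasibility and be visible beside the safety result. If it is a comparison between conditions, equally low wear in both months could pass. The wording allows either reading, so the protection is partial.
- **Low wear can act in the other direction.** Poor wear confined to the control month would remove events caused by the wristband from that side only, making treatment look worse. This is possible, but the plan has no analysis that would reveal either pattern.

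**Conclusion.** The concern holds as a matter of direction: with intent to treat as the only named safety analysis, low wear in the treatment month biases the comparison towards safety, and nothing in the plan ties the conclusion to exposure. That intent to treat is the only set is inferred from the absence of any other; the plan does not expressly rule one out.

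The size is modest at mild non-wear. Relative to 4.7% at full wear, the false non-inferiority rate is between 5.9% (half the excess retained) and 7.5% (none retained) with 3 of 24 affected. It becomes serious only if a quarter or more are effectively unexposed. These figures rest on a one-sided 5% score test, 5% control-only events and a true 20-point excess in wearers.

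A reader might also infer that intent to treat is the wrong primary analysis, or that safety should be concluded only if compliant participants pass too. Neither follows: dropping people who cut wear because of an event would hide harm, and a second required test would cost power.

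**What to change.** Keep intent to treat as the primary safety analysis. Before unblinding, add to section 10.0:

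1. A supporting paired analysis in participants who meet the plan's own compliance definition in both months, reported with its estimate and confidence interval. Participants who reduced or stopped wear because of an adverse event are kept in and counted as events.
2. A table of adverse events by logged hours of wear in the treatment month.
3. A statement that, if compliance is low or the two analyses differ, the safety conclusion is limited to the wear actually achieved.

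Do not make the compliant set a formal second gate. With no true difference, and compliance unrelated to events, power for that set alone is 77.0% at n = 21, 63.2% at n = 18 and 57.8% at n = 12, against 82.4% at 24. Requiring both analyses to pass would give about 75%, 62% and 55%.

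The cost is SAP wording and one extra analysis of data already being collected, with no new visits or participants. The compliant set will be smaller, self-selected and dependent on self-reported wear with only a rough pedometer check, so it can inform the conclusion but not carry it.

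### The claim to be powered to discern different adverse event rates above 3 of 24 is not supported by the power analysis, which is sized only for non-inferiority

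*Combined protocol and SAP*

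**What the plan says.** All the relevant text is in section 10.0 Data Management of the combined protocol and SAP.

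- The statistical analysis bullet names one test for the primary aim, comparing rates "between the treatment and control conditions using the test of non-inferiority".
- It sets the size of interest: "The meaningful difference in adverse events to detect between the treatment and control is 20" per cent.
- It then says, resting on the power analysis further down, that "we will be sufficiently powered to statistically discern different rates of adverse events if more than 3 out of 24 participants experience adverse events" in treatment versus control.
- The next sentence restates this as a decision rule: "if 3 or less participants out of 24 experience adverse events in the treatment vs. control condition, we will deem TheraBracelet safe".
- The power analysis bullet describes the calculation as "testing hypothesis of non-inferiority using a 2×2 crossover at 80% power and 5% significance level", and concludes: "A sample size of 24 (12 in each condition at randomization) provides sufficient power to conclude non-inferiority". Its inputs are given as "assuming a total of 10% discordance rate (proportion of participants with different responses for the two conditions) and a 90% safe rate for the control".

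No conclusion is spelled out for more than 3 participants, apart from the sentence about discerning different rates. The sidedness of the 5% level is not stated.

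**The concern.** Showing non-inferiority and detecting a difference are separate inferences with separate power. A trial that fails to show non-inferiority is inconclusive: the rates may differ, or there may be too little information. The statistical analysis text treats crossing the limit as a powered detection of different rates and credits this to a calculation that does not address it.

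This is the primary safety outcome, and the sentence is the plan's only guidance on what more than 3 participants with events means. A reader could take four events as a statistically established excess, or could believe that the trial has adequate power to detect a 20-point excess.

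**Working it through.** **Inputs (section 10.0).** N = 24, each participant receiving both conditions; margin and meaningful difference 20%, read as absolute points; 10% total discordance; 90% safe on control, so a 10% event rate; 80% power; 5% significance.

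**1. The plan's own figure.** Take a paired non-inferiority score test, one-sided 5%, with true difference 0 and treatment-only and control-only rates of 0.05 each. With d = 0.20, the restricted control-only rate is q = [√(0.3² + 4·2·0.008) − 0.3]/4 = 0.0231. The null variance is 2q + d(1 − d) = 0.0462 + 0.16 = 0.2062.

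N = (1.645·√0.2062 + 0.842·√0.10)² / 0.20² = 25.7, so 26. Exact power at N = 24 is 82.4%. The stated 24 is therefore reasonable as a non-inferiority size. Nothing in this calculation concerns detecting a difference. Its 10% discordance could not describe a 20-point excess in any case, since a paired difference cannot exceed total discordance.

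**2. Does four against none show a difference?** Let b be the number of participants with events only on treatment and c the number only on control. The exact McNemar test refers b to Binomial(b + c, ½).

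- 4 vs 0: two-sided p = 2·(½)⁴ = 0.125; one-sided p = 0.0625.
- 4 vs 0, uncorrected: (4 − 0)²/4 = 4.0, two-sided p = 0.0455.
- 4 vs 1: exact two-sided p = 2·(1 + 5)/32 = 0.375; uncorrected 3²/5 = 1.8, p = 0.180.
- Exact two-sided significance first arrives at 6 vs 0 (2/64 = 0.031) or 8 vs 1 (2·10/512 = 0.039).

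**3. Power for a true 20-point excess at N = 24.** This sums the trinomial probabilities of all (b, c) that reject at 5%. The plan gives no discordance under a true difference, so the control-only rate is an assumption, shown over a range.

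| Treatment-only / control-only rate | 20% / 0 | 22.5% / 2.5% | 25% / 5% |
|---|---|---|---|
| Exact, two-sided | 34% | 32% | 28% |
| Uncorrected, two-sided | 74% | 55% | 44% |
| Exact, one-sided | 54% | 47% | 41% |
| Uncorrected, one-sided | 88.5% | 68% | 59% |

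The first column can be checked by hand, because b is then Binomial(24, 0.20): P(b ≥ 6) = 0.344, P(b ≥ 5) = 0.540, P(b ≥ 4) = 0.736 and P(b ≥ 3) = 0.885. The 88.5% belongs to a test that already rejects at 3 vs 0 (3/√3 = 1.73 > 1.645). It is not the power of a cut at more than 3; read as 4 or more treatment-only events, that cut is crossed 73.6% of the time in this column.

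**4. If the limit is a raw treatment count.** With a true treatment rate of 10%, equal to the rate assumed for control, P(X ≥ 4) for Binomial(24, 0.10) = 1 − 0.786 = 0.214.

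**The case against.** The best defence is that the sentence is a loose paraphrase. The only named test is non-inferiority, the next sentence restates the rule in those terms, and the power analysis is worded correctly. On that reading no second hypothesis is being tested. This stands as far as intent goes. It does not make the sentence true: the two sentences are not equivalent, and nothing else in the plan says what exceeding 3 means.

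It is also fair that two-sided testing is a choice. The plan leaves sidedness open, and one-sided 5% is what reproduces its sample size. The one-sided rows are shown for that reason. If the limit is read as a net excess (b − c above 3), it is crossed under equal rates only 1.3% of the time at 10% discordance and 5.3% at 20%. On that reading crossing carries some weight, but a 20-point excess crosses it only 74%, 71% and 70% of the time in the three columns above, still under 80%.

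Three stronger readings are tempting, and the documents do not support them:

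- **That no difference test could reach 80% at N = 24.** The uncorrected one-sided McNemar test does when there are no control-only events.
- **That the plan would report more than 3 as proven harm.** It states a conclusion only for 3 or fewer, and nothing ties the monitoring board's judgement to this sentence.
- **That the cut came from an uncorrected McNemar result for 4 vs 0.** The plan names no such test. A single-arm exact rule of 10% versus 30% also gives a limit of 3 (error 4.2%, power 78.6%).

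**Conclusion.** The point holds as a stated power that the cited calculation does not provide. For a true 20-point excess at N = 24, two-sided power falls short of 80% by 46 to 52 points (exact) or 6 to 36 points (uncorrected), and exact one-sided power by 26 to 39 points. The single exception needs an uncorrected one-sided test and no control-only events at all. Crossing the limit does not by itself establish different rates, and a reader could misread it as doing so.

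This rests on reading 20% as absolute points, on all 24 participants contributing paired data, and on control-only rates of 0 to 5%. It does not affect the sample size, the data collected or the rule for 3 or fewer. Whether that limit agrees with the non-inferiority test is a separate question.

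**What to change.** In the statistical analysis part of section 10.0:

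- Delete the claim about discerning different rates when more than 3 of 24 have events.
- State that the sizing covers the non-inferiority conclusion only, and that exceeding the limit means non-inferiority was not shown, which is inconclusive and not evidence of a difference.
- Report the paired difference in adverse event rates with an exact confidence interval, whatever the result.
- If any power to detect a difference is quoted, give the test, its sidedness and the assumed discordance with it.

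The cost is a few sentences and one extra interval, with no added participants or visits. The downside is that the capability the plan states for itself becomes less favourable.
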